#### **8.3.1.2.1 Assessment of Severity**

The severity, or intensity, of an AE refers to the extent to which an AE affects the participant's daily activities. The intensity of the AE will be rated as mild, moderate, or severe using the following criteria:

Mild: These events require minimal or no treatment and do not interfere with the participant's daily activities.

OR

An event usually transient in nature and generally not interfering with normal activities.

Moderate: These events result in a low level of inconvenience or concern with the therapeutic measures. Moderate events may cause some interference with normal functioning. Usually alleviated with additional specific therapeutic intervention.

OR

An AE that is sufficiently discomforting to interfere with normal activities.

Severe: These events interrupt a participant's usual daily activity and may require intensive therapeutic intervention. Severe events are usually incapacitating.

OR

An AE that is incapacitating and prevents normal activities.

The term "severe" is often used to describe the intensity of a specific event (as in mild, moderate, or severe myocardial infarction); the event itself, however, may be of relatively minor medical significance (such as severe headache). This criterion is not the same as "serious", which is based on participant/event outcome or action criteria associated with events that pose a threat to a participant's life or functioning.

Seriousness, not severity, serves as a guide for defining regulatory obligations.

Changes in the severity/intensity of an AE should be documented to allow an assessment of the duration of the event at each grade of severity/intensity. AEs characterized as intermittent do not require documentation of onset or duration of each episode.

### **8.3.1.2.2 Assessment of Causality**

The investigator must assess the relationship between the study treatment and the occurrence of each unsolicited AE (including SAEs) using clinical judgment. Where several different study treatments are administered, the investigator should specify, when possible, if the unsolicited AE could be causally related to a specific study treatment. When a causal relationship to a specific study treatment cannot be determined, the investigator should indicate that the unsolicited AE is related to all study treatments.

Alternative possible causes, such as the natural history of underlying disease, concomitant therapy, other risk factors, and the temporal relationship of the event to the study treatment will be considered and investigated. The investigator will also consult the IB and/or

Summary of Product Characteristics and/or Prescribing Information for marketed products to assist in making their assessment.

Causality should be assessed by the investigator using the following question, and the answer recorded in the eCRF: Is there a reasonable possibility that the unsolicited AE may have been caused by the study treatment?

**YES:** There is a reasonable possibility that the study treatment contributed to the AE.

**NO:** There is no reasonable possibility that the AE is causally related to the administration of the study treatment. There are other, more likely causes and administration of the study treatment is not suspected to have contributed to the AE.

If an event meets the criteria to be determined an SAE ([Section 8.3.1.1.2](#)), additional examinations/tests will be performed by the investigator to determine **all** possible contributing factors for each SAE.

Possible contributing factors include:

- Medical history.
- Other medication.
- Protocol-required procedure.
- Other procedure not required by the protocol.
- Lack of efficacy of the IP, if applicable.
- An error in IP administration.
- Other cause (specify).

There may be situations when an SAE has occurred, and the investigator has minimal information to include in the initial report to the sponsor. However, it is very important to record an assessment of causality for every event before submitting the Expedited Adverse Events Report to the sponsor.

The causality assessment is 1 of the criteria used when determining regulatory reporting requirements. The investigator may change their opinion of causality after receiving additional information and update the SAE information accordingly.

The investigator's assessment of an AE's relationship to study treatment is part of the documentation process, but it is not a factor in determining what is or is not reported in the study. If there is any doubt as to whether a clinical observation is an AE, the event should be reported.

### **8.3.1.3 Reporting Adverse Events**

All AEs reported or observed during the study will be recorded on the AE page in the eCRF.

The AEs resulting from concurrent illnesses, reactions to concurrent illnesses, reactions to concurrent medications, or progression of disease states must also be reported. All AEs will be followed to adequate resolution. Medical Dictionary for Regulatory Activities (MedDRA) will be used to code all AEs.

Any medical condition that is present at the time that the participant is screened but does not deteriorate should not be reported as an AE. However, if the medical condition deteriorates at any time during the study, it should be recorded as an AE.

#### **8.3.1.3.1 Reporting Serious Adverse Events**

Any AE that meets the SAE criteria ([Section 8.3.1.1.2](#)) must be reported to Lilly immediately (ie, within 24 hours) after study site staff first learn of the event. If an SAE is determined to be related to study procedure(s) occurring at a study site visit before administration of the study treatment, the SAE will be reported before administration of the study treatment. Initial notification via telephone does not replace the need for the investigator to complete and sign the SAE form within the designated reporting time frames.

The sponsor has a legal responsibility to notify both the local regulatory agency and other regulatory agencies about the safety of a study treatment under clinical investigation. The sponsor will comply with country-specific regulatory requirements relating to safety reporting to the regulatory authority, IRB/IEC, and investigators.

An investigator who receives an investigator safety report describing an SAE or other specific safety information from the sponsor will review and then file it as appropriate and will notify the IRB/IEC, if appropriate according to local requirements.

If a participant dies during participation in the study or during the recognized SFU period, the investigator will provide the sponsor or designee with a copy of any postmortem findings including histopathology.

### **8.3.1.3.2 Reporting Suspected Unexpected Serious Adverse Reactions**

The sponsor will promptly evaluate all SUSARs and nonserious AESIs against cumulative study treatment experience to identify and expeditiously communicate possible safety findings to investigators, IRBs/IECs, and applicable regulatory agencies based on applicable legislation.

The sponsor has processes for safety reports for identification, recording, and expedited reporting of SUSARs according to EU regulatory requirements. The sponsor will comply with applicable regulatory requirements relating to safety reporting to the regulatory authority, per European Union Clinical Trial Regulation 536/2014 submission of SUSARs to the EudraVigilance database.

An investigator who receives an investigator safety report describing an SAE or other specific safety information (eg, summary or listing of SAEs) from the sponsor will review and then file it along with the IB and will notify the IRB/IEC, if appropriate according to local requirements.

To determine reporting requirements for single AE cases, the sponsor will assess the expectedness of these events using the reference safety information in the lebrikizumab IB or any available label for lebrikizumab at the time.

The sponsor will compare the severity of each SUSAR and the cumulative event frequency reported for the study with the severity and frequency reported in the applicable reference document.

Reporting requirements will also be based on the investigator's assessment of causality and seriousness, with allowance for upgrading by the sponsor as needed.

### **8.3.1.4 Follow-Up of Participants Reporting Adverse Events**

All AEs must be reported in detail on the appropriate page in the eCRF and followed to satisfactory resolution, until the investigator deems the event to be chronic or not clinically significant, the event is considered to be stable, or the participant is lost to follow-up. For product complaints ([Section 8.3.1.1.3](#)), the investigator is responsible for ensuring that follow-up includes any supplemental investigations as indicated to elucidate the nature and/or causality of the AE.

The investigator is obligated to perform or arrange for the conduct of supplemental measurements and/or evaluations as medically indicated or as requested by the sponsor or designee to elucidate the nature and/or causality of the AE or SAE as fully as possible. This may include additional laboratory tests or investigations, histopathological examinations, or consultation with other health care professionals.

The investigator will record new or updated information in the original completed eCRF and will submit any updated SAE data to sponsor, or designee, within 24 hours of receipt of the information.

### **8.3.2 Clinical Safety Laboratory Assessments**

Refer to [Appendix 15.4](#) for the list of clinical laboratory tests to be performed and to the SoA ([Table 1-1](#)) for the timing and frequency of sampling during the study.

The investigator must review the laboratory report and document this review. The laboratory reports must be filed with the source documents.

Any clinically significant safety findings that are associated with the underlying disease, unless judged by the investigator to be more severe than expected for the participant's condition, are not to be reported as AEs or SAEs.

Venous blood and urine samples are obtained for clinical safety laboratory tests including hematology, clinical chemistry, and urinalysis evaluations. All samples are to be sent to the central laboratory for analysis of the following parameters presented in [Appendix 15.4](#).

In exceptional circumstances, to ensure participant safety and with the sponsor's prior written approval, local laboratory testing may be conducted in lieu of central laboratory testing.

However, central laboratory testing must be retained for PK, biomarkers, and immunogenicity (ADA) samples.

Abnormal laboratory findings discovered during the screening period should be recorded on the medical history page in the eCRF in the form of a diagnosis. Actual laboratory values should not be recorded. All participants with laboratory results with clinically significant abnormal values are followed regularly until the values return to normal ranges or until a valid reason, other than study treatment-related AEs, is identified. If such values do not return to normal/baseline within a period of time judged reasonable by the investigator, the etiology should be identified, and the sponsor notified.

For laboratory parameters for each panel (hematology, clinical chemistry, urinalysis), please refer to the laboratory manual. If the laboratory reports are not transferred electronically, the values must be filed with the source information (including reference ranges). In most cases, clinically significant abnormal laboratory findings are those that are not associated with the underlying disease, unless judged by the investigator to be more severe than expected for the participant's condition.

The local laboratory must be qualified in accordance with local regulations. All protocol-required laboratory assessments must be conducted in accordance with the laboratory manual and the SoA ([Table 1-1](#)).

### **8.3.3 Physical Examinations**

A complete physical examination will be conducted at screening and must include assessment of the cardiovascular, respiratory, gastrointestinal, and neurologic systems, as well as the skin.

Targeted physical examinations may be conducted at study site visits to address intercurrent AEs. Investigators should pay special attention to clinical signs related to previous serious illnesses or concurrent conditions.

### **8.3.4 Height**

Height will be measured at screening and recorded to 1 decimal place without rounding. The instruments used for measuring height should be appropriately and regularly calibrated. Height for adolescents will also be measured whenever vital signs and weight are assessed

according to the SoA (Table 1-1) to evaluate participants' growth over time.

### **8.3.5 Vital Signs and Weight**

Vital signs, including body temperature, respiratory rate (breaths per minute), pulse (beats per minute), and blood pressure (mm Hg), will be obtained with the participant in the seated position, after sitting for at least 5 minutes. Vital sign measurements will be recorded in the eCRF.

Weight will be measured according to the SoA (Table 1-1) and recorded to 1 decimal place without rounding. The instruments used for measuring weight should be appropriately and regularly calibrated. All measurements of weight should be made without shoes and after the removal of any heavy personal items (ie, heavy jewelry, wallets, coats, etc.).

### **8.3.6 Electrocardiograms**

Electrocardiograms will not be performed in this study.

### **8.3.7 Other Safety Assessments**

#### **8.3.7.1 Chest Imaging**

Chest x-rays will be conducted as a screening requirement in this study to assess baseline chest health and detect preexisting conditions or abnormalities. A locally performed chest x-ray (posterior–anterior view and, if needed, a lateral view) is required for screening (Visit 1) as specified in the SoA (Table 1-1), unless one has been performed within 12 months of screening (Visit 1) and the report is available for review by the investigator.

For countries that require x-ray for TB assessment, study sites will follow local guidelines. For countries that require an additional TB assessment (ie, QuantiFERON), local guidelines will be followed.

#### **8.3.7.2 Suicidal Ideation and Behavioral Risk Monitoring**

Not applicable to this study.

### **8.3.7.3 Injection Site Reactions**

Symptoms of a local ISR may include erythema, induration, pain, pruritus, and edema. If an injection site event is reported, it will be recorded as an AE on the appropriate page in the eCRF.

Additional ISR characterization data will be collected on the ISR-specific page in the eCRF.

### **8.3.7.4 Systemic Hypersensitivity Reactions**

Many drugs, but particularly biologic agents, carry the risk of systemic hypersensitivity reactions. If such a reaction occurs, additional data describing each symptom should be provided in the eCRF on the page specific to systemic hypersensitivity reactions.

Study sites should have appropriately trained medical staff and appropriate medical equipment available when study participants are receiving the study treatment. It is recommended that participants who experience a systemic hypersensitivity reaction be treated per national and international guidelines.

In the case of generalized urticaria or anaphylaxis, additional blood and urine samples will be collected as described in [Appendix 15.5](#). Laboratory results are provided to the sponsor via the central laboratory.

### **8.3.7.5 Eosinophil-Related Disorders**

A specific eCRF will be used to collect additional data on potential events of eosinophil-related disorders.

The completion of the eCRF page will be conducted by the investigator and will be triggered by:

- Any TEAE of eosinophil-related disorder or,
- A laboratory result of severe eosinophilia (eosinophil count >5000 eosinophils/ $\mu$ L)

The objective is to collect sufficient information for an accurate and complete characterization of any eosinophil-related disorders that may be reported during the study.

### 8.3.7.6 Hepatitis Testing and Monitoring

#### Hepatitis B Testing

Initial testing for HBV infection includes:

- HBsAg;
- Anti-hepatitis B core; and
- Anti-hepatitis B surface.

As specified in the SoA ([Table 1-1](#)), initial testing for HBV infection includes HBsAg and hepatitis B core antibody (HBcAb) for the following reasons:

- If HBsAg is positive, the participant is excluded.
- If HBsAg is negative and HBcAb is negative, the participant is not excluded.
- If HBsAg is negative and HBcAb is positive, further testing for HBV DNA is required.
  - If the screening HBV DNA is positive, the participant is excluded.
  - If the screening HBV DNA is negative, the participant is not excluded. Repeat testing for HBV DNA is required at least every 3 months during the study as described in the SoA ([Table 1-1](#)).

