Participant eDiaryl													
Participant eDiary dispensed l		X											
Participant eDiary compliance check m			X	X	X	X	X	X	X	X	X	X	
Participant eDiary return											X		
Patient-Reported Outcomes/Health-Related Quality of Life (electronic device, site-based)													
VAS of CRS			X	X	X		X		X		X	X	
SNOT-22			X		X		X		X	X	X	X	
ACQ-6 n			X		X				X		X	X	
EQ-5D-5L			X						X		X	X	
WPAI+CIQ:CRS w NP			X						X		X	X	

CRSwNP 72 Week  Visit number  Weeks from randomization  Days from randomization  Activity Visit interval tolerance (days)	Screening	Run-In	Randomized a Treatment Period								EOT/ET	UV	SFU
	1	2	3	4	5	6	7	8	9	10	11	UV b	801
	W-8 to W-4	W-4 to W0	Baseline	W2	W4	W6	W8	W16	W24	W40	W56	NA	W64 or 12 weeks after last dose
	D-58 to D-28	D-28 to D0	D0	D14	D28	D42	D56	D112	D168	D280	D392	NA	D448
	--	--	±3	±3	±3	±3	±3	±3	±3	±5	±5	NA	±5
PROMIS Short Form v1.0 – Anxiety 8a			X						X		X	X	
PROMIS Short Form v1.0 – Depression 8a			X						X		X	X	
PGI-S: nasal congestion			X	X	X	X	X	X	X	X	X	X	
PGI-S: loss of smell			X	X	X	X	X	X	X	X	X	X	
PGI-S: postnasal drip			X	X	X	X	X	X	X	X	X	X	
PGI-C: nasal congestion									X		X	X	
PGI-C: loss of smell									X		X	X	
PGI-C: postnasal drip									X		X	X	
Safety													
Adverse events o	X	X	X	X	X	X	X	X	X	X	X	X	X
Concomitant medications	X	X	X	X	X	X	X	X	X	X	X	X	X
Record rescue medication intervention				X	X	X	X	X	X	X	X	X	X
Laboratory Testing													
Pregnancy test (for WOCBP and all female adolescents) p	X		X		X		X	X	X	X	X		X
Hematology/clinical chemistry laboratory	X		X		X		X	X	X	X	X		
Urinalysis	X								X		X		
HCV, HBV, HIV tests	X												
HBV DNA q	X							X	X	X	X		
Immunogenicity (ADA) sample			X		X			X	X		X		X
Total immunoglobulin E			X		X			X	X		X		

Activity	CRSwNP 72 Week	Screening	Run-In	Randomized a Treatment Period							EOT/ET	UV	SFU	
	Visit number	1	2	3	4	5	6	7	8	9	10	11	UV b	801
	Weeks from randomization	W-8 to W-4	W-4 to W0	Baseline	W2	W4	W6	W8	W16	W24	W40	W56	NA	W64 or 12 weeks after last dose
	Days from randomization	D-58 to D-28	D-28 to D0	D0	D14	D28	D42	D56	D112	D168	D280	D392	NA	D448
	Visit interval tolerance (days)	--	--	±3	±3	±3	±3	±3	±3	±3	±5	±5	NA	±5
	Pharmacokinetics s			X		X			X	X	X	X		X
	TB assessment (country-specific) †	X												
Stored Samples														

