- o. Includes assessments of all AEs. AEs will be assessed from the time the participant signs the ICF and up until participation in the study has ended ([Section 8.3.1](#)).
- p. Pregnancy tests will be conducted only for individuals of childbearing potential and all female adolescents: serum testing at screening and urine testing at subsequent visits prior to administering any IP. Refer to [Section 8.4](#) for details on reporting positive pregnancy test results obtained away from the study site. Additional pregnancy tests (beyond those required by the SoA) should be performed at any time during the study if a menstrual period is missed or there is clinical suspicion of pregnancy. If required per local regulations and/or institutional guidelines, pregnancy testing can occur at other times during the study treatment period.
- q. If HBsAg is negative and HBcAb is positive at screening, further testing for HBV DNA is required ([Section 7.1](#), [Section 7.1.2](#), [Section 7.2.1](#), and [Section 8.3.7.6](#), and [Appendix 15.2](#) and [Appendix 15.4](#)).
- r. NPIF and spirometry should be performed prior to endoscopy.
- s. Blood samples will be collected before dosing of IP on a dosing day.
- t. For countries that require an additional TB assessment (ie, QuantiFERON), local guidelines will be followed.
- u. Genetic samples will be collected for exploratory research where local regulations allow ([Section 8.9](#)).

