**Table 6-1 Study Treatments Administered**

Study Treatment	Lebrikizumab	Placebo	Mometasone Furoate
Study Treatment Name	LY3650150	Placebo to match	INCS
Dose Formulation	PFS-NSD to deliver 2.0 mL	PFS-NSD to deliver 2.0 mL	Metered spray
Unit Dose Strength(s)	250 mg, 125 mg/mL	Matched PBO, lacking lebrikizumab	50 µg per spray
Dosage Level(s)	500 mg (2 PFS-NSD) loading dose	2 PFS-NSD loading dose	200 µg (2 sprays in each nostril), BID
	250 mg (1 PFS-NSD) induction and maintenance dose	1 PFS-NSD induction and maintenance dose	
Route of Administration	Subcutaneous injection	Subcutaneous injection	Nasal spray
Authorized as Defined by EU CTR	Not authorized	Not authorized	Authorized and used according to authorization

Note: Placebo study treatment is only applicable for adult participants.

Abbreviations: BID = twice daily; EU CTR = European Union Clinical Trials Register; INCS = intranasal corticosteroid; PBO = placebo; PFS-NSD = prefilled syringe with needle safety device.

The schedules for administration of blinded lebrikizumab Q2W/Q4W arm, lebrikizumab Q2W/Q8W arm, and PBO arm are presented in [Table 6-2](#) and [Table 6-3](#)). Study sites will dispense study treatment for administration at home according to the SoA ([Table 1-1](#)). Study treatments will be supplied in accordance with current Good Manufacturing Practice. IP will be labeled as appropriate for country requirements.

Background medications will be dispensed to all participants for use throughout the study, according to the SoA ([Table 1-1](#)). Further details on dosing of background interventions are presented in [Section 6.10.2.2](#). Participants who are not comfortable self-administering IP away from the study site may come to the study site for administration according to the “away” administration schedule. Refer to [Section 4.1](#) for randomization and treatment assignments.

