### **7.1.2 Temporary Interruption of Investigational Product**

Some possible reasons for temporarily withholding the IP include, but are not limited to:

- Serious or opportunistic infections ([Section 5.2](#) and [Appendix 15.3](#)). The IP is to be withheld until resolution of all acute clinical signs and symptoms, and completion of all appropriate anti-infective treatment.
- HBV DNA results are reported as positive, or as detecting HBV DNA, but HBV DNA is below the level of quantification. The sponsor's designated medical monitor should be contacted regarding study status of the participant. HBV DNA testing is to be repeated as soon as is feasible. If HBV DNA is confirmed as positive, the participant must be permanently discontinued from IP ([Section 7.2.1](#)).
- Hepatic event abnormalities are presented in [Section 8.3.7.6](#).
- Liver test abnormalities are presented in [Section 8.3.7.7](#).

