## 15.4 Clinical Laboratory Tests

General guidance for clinical laboratory testing ([Table 15-1](#)) includes the following:

- The tests detailed in the table below will be performed by the central laboratory.
- In circumstances where the sponsor approves local laboratory testing in lieu of central laboratory testing (in the table below), the local laboratory must be qualified in accordance with applicable local regulations.
- Protocol-specific requirements for inclusion or exclusion of participants are detailed in [Section 5](#) of the protocol.
- Additional tests may be performed at any time during the study as determined necessary by the investigator or required by local regulations.
- Investigators must document their review of the laboratory safety results.

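### The Schedule of Activities does not deliver the 3-monthly HBV DNA testing that Section 8.3.7.6 says it contains: three of its four intervals are 16 weeks or longer

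*Protocol*

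**What the plan says.** Section 8.3.7.6 (Hepatitis B Testing) admits participants who are HBsAg-negative and HBcAb-positive if their screening HBV DNA is negative. For them it sets a monitoring rule: "Repeat testing for HBV DNA is required at least every 3 months during the study as described in the SoA".

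Table 1-1 marks the HBV DNA row at Visits 1, 8, 9, 10 and 11 only, that is, screening, W16, W24, W40 and W56. The last four fall on "D112 D168 D280 D392". Footnote q to that row says who is tested ("If HBsAg is negative and HBcAb is positive at screening, further testing for HBV DNA is required") and refers back to Section 8.3.7.6, among others. It names no further visits. Table 15-1 likewise says only who is tested.

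The result has consequences. Section 7.1.2 has study drug withheld when HBV DNA is reported positive or detected below the level of quantification, and then: "If HBV DNA is confirmed as positive, the participant must be permanently discontinued from IP". Section 7.2.1 also lists HBV DNA positivity under mandatory withdrawal from the study.

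**The concern.** The text sets a maximum interval and attributes it to the schedule, but the schedule has longer intervals. The cross-references are circular: Section 8.3.7.6 points to the SoA, and the SoA footnote points back to Section 8.3.7.6. Section 8 makes adherence to the SoA mandatory and disallows waivers, so sites will work from the table. A site that follows it exactly breaches Section 8.3.7.6 for every participant in this subset who stays to W56.

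What is at stake is safety monitoring. Appendix 15.3 lists hepatitis B reactivation among infections that may be considered opportunistic under biologic therapy, and the HBV DNA test is the trigger for interrupting drug. Before W16, scheduled chemistry at baseline, W4 and W8 gives some cover through ALT and AST. In maintenance it gives none between tests, because chemistry and HBV DNA are scheduled at the same visits (9, 10 and 11) and the doses in between are given away from the site (Table 6-3).

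**Working it through.** **Inputs, all from Table 1-1.** Visit 1: D-58 to D-28. Visit 5 (W4): D28 ±3. Visit 8 (W16): D112 ±3. Visit 9 (W24): D168 ±3. Visit 10 (W40): D280 ±5. Visit 11 (W56): D392 ±5. Three months is taken as 365.25/4 = 91.3 days.

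**Formula.** Nominal interval = day of later test − day of earlier test. The shortest interval puts the earlier visit at the end of its window and the later one at the start; the longest does the reverse.

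**Intervals as scheduled**

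| Interval | Nominal (days) | Shortest | Longest | Within 91? |
|---|---|---|---|---|
| Screening to W16 | 112+28 = 140 to 112+58 = 170 | 109+28 = 137 | 115+58 = 173 | No |
| W16 to W24 | 168−112 = 56 | 165−115 = 50 | 171−109 = 62 | Yes |
| W24 to W40 | 280−168 = 112 | 275−171 = 104 | 285−165 = 120 | No |
| W40 to W56 | 392−280 = 112 | 387−285 = 102 | 397−275 = 122 | No |

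The 3-month figure is not reproduced. In weeks the nominal intervals are 20 to 24.3, 8, 16 and 16.

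**Time on drug.** The screening-to-W16 interval includes 28 to 58 days before the first dose. No HBV DNA test is scheduled at W0, so drug exposure before the first repeat test is D0 to D112 = 112 days. The longest nominal on-treatment stretch without a test is therefore 112 days, and it occurs three times (W0–W16, W24–W40, W40–W56). The excess is 112 − 91 = 21 days each time.

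**Intervals with W4 added**
- Screening to W4: 28+28 = 56 to 28+58 = 86 days; at most 31+58 = 89 with windows.
- W4 to W16: 112−28 = 84 days; 109−31 = 78 to 115−25 = 90 with windows.

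Both comply. W8 (D56) alone would not be enough: screening to W8 is 56+28 = 84 to 56+58 = 114 days.

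**Intervals with W32 (D224) and W48 (D336) added.** 224−168, 280−224, 336−280 and 392−336 are each 56 days nominally.

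**The case against.** The strongest reply is that the texts can be reconciled in practice. Appendix 15.4 says: "Additional tests may be performed at any time during the study as determined necessary by the investigator". A site that reads Section 8.3.7.6 closely can order the missing tests and satisfy both texts. This is true, but a permission is not a schedule: Section 8.3.7.6 says the SoA already contains the interval, and it does not.

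Other points have some force:

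- **Pre-treatment time.** The 20 to 24 weeks includes time before any drug is given. The safety-relevant figure is 16 weeks, about 3 weeks over.
- **Reactive safeguards.** Unscheduled visits and repeat safety samples (Section 8) remain available, and a comprehensive hepatic evaluation, once triggered, includes hepatitis B testing (Section 8.3.7.9). These respond to a signal already seen and do not replace routine testing. What is missing in maintenance is scheduled cover.
- **Wider windows.** Appendix 15.6 allows larger visit windows in exceptional circumstances. Added to the ordinary windows and used in opposite directions, they could shorten the two maintenance gaps to (280−12)−(168+10) = 90 and (392−12)−(280+12) = 88 days. That is an emergency provision, not the planned schedule.
- **Scope.** Only one serological subset is affected, and its size is not stated.

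These points limit the impact. None of them removes the contradiction.

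**Conclusion.** The concern holds. Section 8.3.7.6 and Table 1-1 contradict each other, and three of the four scheduled HBV DNA intervals exceed 3 months at any spacing the ordinary windows permit. The nominal on-treatment excess is about 21 days per gap. This rests on reading 3 months as about 91 days and on the marked cells of the HBV DNA row.

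It should be fixed because the test governs withholding and stopping study drug, and because the present wording builds in deviations for sites that follow the table. It affects only HBsAg-negative, HBcAb-positive participants whose screening HBV DNA was negative. Sample size, power, type I error and the efficacy analyses are untouched.

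**What to change.** 1. **Up to W16.** Add HBV DNA for this subset to the W4 (Visit 5) blood draw, which already takes place. The W4-to-W16 interval then has little slack (up to 90 days with windows); adding W8, also an existing draw, would give more room.
2. **Maintenance.** Choose one rule:
   - keep 3 months and add draws at about W32 and W48; or
   - have the sponsor's safety physicians justify a 16-week interval and restate it in Section 8.3.7.6.
3. **Where to state it.** Put the chosen visits in the HBV DNA row or footnote q, and tell sites which rule applies to any participants already enrolled.

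W32 and W48 are away-dosing weeks. Section 6.1 provides that "Participants who are not comfortable self-administering IP away from the study site may come to the study site for administration", but this does not make them laboratory visits, so for most participants they would be extra attendances.

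**Cost.** A text and SoA correction. Keeping the 3-month rule adds three tests (W4, W32, W48) and up to two attendances per affected participant; W8, if used, adds a fourth test but no visit. The protocol does not give the size of the subset. If it is assumed to be 1% to 10% of the 510 adults (0.01 × 510 ≈ 5 to 0.10 × 510 = 51), three tests each come to about 15 to 153 in total. Any adolescents in the subset would add to this. Restating a 16-week maintenance interval instead leaves only the W4 test.
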